2.32 Comparison of Imaging and Surgical Findings

To compare the extent of disease described on imaging (mammography, bilateral breast MRI and other adjunctive imaging modalities) with surgical findings.

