3.14 Foci of Breast Cancer

Upon clinical exam and pre-operative imaging by mammogram +/- MRI, two or three foci of biopsy proven breast cancer separated by ≥ 2 cm of normal breast tissue.

Foci must include *at least one focus of invasive breast carcinoma with another focus of either invasive breast carcinoma or ductal carcinoma in situ (DCIS)*.

No more than 2 quadrants with biopsy proven breast cancer.

Note: The shortest distance between lesions must be reported on mammogram +/- MRI and eligibility criteria must be met on both, if both are obtained.

Note: Patient is eligible for study if lesion is not visualized on all imaging modalities (i.e., any of the lesion(s) is/are visualized on MRI but not on mammogram OR visualized on mammogram but not on MRI). Ultrasound cannot be used to determine patient eligibility; eligibility to be determined by bilateral mammogram +/- MRI **only**. Fine needle aspirate of the second or third lesion to document malignancy is allowed if the first focus is shown to be invasive by core needle biopsy. Patient may remain on study if, upon pathological assessment, two or three lesions identified on pre-operative imaging represent one contiguous lesion.

3.15 Patients may be registered AFTER surgery and PRIOR TO radiation therapy if either of the criteria is met:

1. An area of atypia > 2 cm from the index lesion excised at the time of cancer operation is upgraded to DCIS or invasive carcinoma thereby identifying MIBC.

OR

2. Patient underwent resection of two or three foci of malignancy by breast conservation surgery with a minimum of one invasive focus of breast cancer and a minimum of 2 cm of normal breast tissue between the lesions on final pathology.

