7.3 Pathology

Margin assessment of each lumpectomy specimen is required. For this study negative margin is defined as no tumor at ink. The size of the closest margin should be measured and reported for each lesion. The anterior and posterior margins are excluded from this restriction if the fascia and/or skin are taken.

When 2 or more lesions are excised en bloc, surgical pathology review is required to assess whether the lesions are separate foci of cancer separated by 2 cm or more of healthy breast tissue.

In consenting patients, tissue from each site of disease within the breast will be submitted for tissue banking and correlative science section. Tissue from axillary lymph nodes (sentinel lymph nodes and/or axillary lymph node dissection dependent on case) will also be collected for correlative science evaluation.

Patient may remain on study if, upon pathological assessment, two or three lesions identified on pre-operative imaging represent one contiguous lesion.

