16.6 Analysis Plan

16.61 Local Recurrence Rate

All eligible patients who have undergone surgery that was not converted to a mastectomy and who did not have a finding of single contiguous area of malignancy on final pathology will be included in the analysis of the primary endpoint.

The cumulative incidence of local recurrences will be estimated in the competing risk framework as described by Marubini and Valsecchi where regional recurrences, distant recurrences and death without a local recurrence will be considered competing risks and contralateral breast and non-breast second primary cancers will not be considered competing risk. A 95 % Poisson confidence interval for the cumulative incidence of a local recurrence within 5 years will be constructed.

Gentilini *et al.* reported that cumulative incidence of local recurrence differed in terms of estrogen receptor status, HER2/neu expression, Nottingham grade, and Ki-67 expression (univariately) (Gentilini *et al.*, 2009). Gray's test will be used to explore whether the cumulative incidence of local recurrence differs with respect to these factors as well as progesterone receptor status, number of positive lymph nodes, number of foci, t-stage, age, perception of quality of life as measured by LASA at registration (poor: 0 to 3; middling: 4 to 7; good/excellent: 8 to 10), and fatigue as measured by LASA at registration (none to little: 0 to 3; some: 4 to 7; a great deal: 8 to 10).

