Impression of cosmesis will be dichotomized as poor to fair versus good to excellent. A 95 % confidence interval will be constructed for the proportion of cases where the patient and his surgeon agree in terms of cosmesis results.

16.664 Differences of the Extent of Disease Described on Mammography Compared with Surgical Findings

All eligible patients who have initiated surgery will be included in the analysis of this endpoint. The maximum lesion dimension and location of each lesion found on mammogram will be determined on central review. Agreement between the lesion size on mammogram and the lesion size reported on surgical pathology report will be examined using the approaches proposed by Bland and Altman. That is, a plot of the average of lesion size on mammogram and the lesion size reported on surgical pathology report versus the difference in lesion size between that found on mammogram and that found on surgery will be constructed to examine systematic biases. A 95 % z-confidence of the difference in lesion size between that found on mammogram and that found on surgery will be constructed. Percent agreement will be used to assess the extent of agreement between location of the lesion seen on mammogram and the location of the lesion reported on surgical pathology report.

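### Section 16.664 compares mammogram and pathology size lesion by lesion, with no rule for foci that prove to be one contiguous lesion and no allowance for several lesions from one woman

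*Combined protocol and SAP*

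**What the plan says.** Goal 2.32 is stated in terms of extent: "To compare the extent of disease described on imaging" with what surgery finds. Section 16.664 carries this out for mammography.

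- Population: "All eligible patients who have initiated surgery will be included in the analysis of this endpoint".
- Imaging measure: "The maximum lesion dimension and location of each lesion found on mammogram will be determined on central review".
- Comparison: "Agreement between the lesion size on mammogram and the lesion size reported on surgical pathology report will be examined", using Bland-Altman methods and a plot of difference against average.
- Interval: "A 95 % z-confidence of the difference in lesion size between that found on mammogram and that found on surgery will be constructed".

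To enter before surgery, a woman needs "two or three foci of biopsy proven breast cancer separated by ≥ 2 cm of normal breast tissue" (section 3.14). Both 3.14 and 7.3 then provide for the case where pathology disagrees: "Patient may remain on study if, upon pathological assessment, two or three lesions identified on pre-operative imaging represent one contiguous lesion". The primary analysis (16.61) is limited to women "who did not have a finding of single contiguous area of malignancy on final pathology". Section 16.664 has no such limit and no separate provision for these women. It also does not say whether the unit of analysis is the lesion or the woman.

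**The concern.** When two imaged foci are one lesion at pathology, there are two mammogram sizes and one pathology size. Section 16.664 does not say whether both foci are compared with that one lesion, only the larger focus is, or neither is. The location agreement has the same gap. The answers differ, and the choice would be made after the data are seen.

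The interval raises a second question. By design a woman has two or three lesions, and a contiguous case may use one pathology value more than once. A plain z-interval over lesions ignores this and would overstate precision.

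A contiguous case is also the most informative disagreement for goal 2.32: imaging showed separate foci where disease was continuous. Section 16.664 does not count how often this happens.

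**Working it through.** Section 16.664 gives no sample size, SD or precision target, so there is no figure of the plan's own to reproduce.

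**Inputs from the documents.** Minimum gap between foci: 2 cm (3.14). The contiguous share is not given. Section 16.3 pools it with consent withdrawal, ineligibility and conversion to mastectomy: 30 of 230 = 13.0% as first planned, and 265 - 200 = 65 of 265 = 24.5% after amendment.

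**Assumptions.** Set A: two foci of 12 mm, 20 mm apart; SD of ordinary differences s = 8 mm with mean 0; contiguous share p = 3, 5 or 10%. Set B: foci of 1 cm; s = 0.5 or 1.0 cm; p from 2 to 24.5%. Within a woman, ordinary errors are taken as independent.

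**Difference for a contiguous case if each focus is compared with the whole lesion.** Set A: span 12 + 20 + 12 = 44 mm, so mammogram minus pathology is D = 12 - 44 = -32 mm. Set B: span 4 cm, so D = 1 - 4 = -3 cm.

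**Effect of the pairing choice.** A share q of pairs has difference D, so mean = qD and SD = sqrt(s² + q(1-q)D²). If both foci are used, q = p. If only the larger focus is used, q = p/(p + 2(1-p)). Set A:

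| p | Both foci: mean; 1.96 SD | Larger focus only: mean; 1.96 SD | Matched lesions only |
|---|---|---|---|
| 3% | -0.96; 19.0 mm | -0.49; 17.5 mm | 0; 15.7 mm |
| 5% | -1.60; 20.8 mm | -0.82; 18.6 mm | 0; 15.7 mm |
| 10% | -3.20; 24.5 mm | -1.68; 21.0 mm | 0; 15.7 mm |

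For set B the spread widens by a factor of 1.08 to 2.77 with both foci, and 1.04 to 2.31 with the larger focus only.

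**Effect on the interval if both foci are paired with the same lesion.** Write V = p(1-p)D². With n women and two lesions each:

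- SE treating lesions as independent: sqrt((s² + V)/(2n))
- SE with woman as the cluster: sqrt((s²/2 + V)/n)
- Ratio: sqrt((s² + 2V)/(s² + V))

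Set A:

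- p = 3%: V = 29.8; sqrt(123.6/93.8) = 1.15
- p = 5%: V = 48.6; sqrt(161.3/112.6) = 1.20
- p = 10%: V = 92.2; sqrt(248.3/156.2) = 1.26

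For an illustrative 200 women (400 lesions), the 95% half-width should be 1.09, 1.25 and 1.54 mm, where the independent calculation gives 0.95, 1.04 and 1.22 mm.

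Set B with s = 0.5 cm, by simulation with 230 women and varying focus sizes: 1.28 (5%), 1.34 (10%) and 1.37 (24.5%). The formula at the same s and p = 2% gives V = 0.176 and sqrt(0.603/0.426) = 1.19. With s = 1.0 cm it gives 1.07 at p = 2% (sqrt(1.353/1.176)) and 1.28 at p = 24.5% (V = 1.665; sqrt(4.330/2.665)).

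**The case against.** A reader might infer that the plan sets each small focus against the whole pathological span, so that limits of agreement are bound to be inflated. The documents do not support this. Section 16.664 contains no such rule. It is silent on pairing, and the inflation depends on how the silence is filled. Limits of agreement are not named either; the z-interval may be meant for the mean difference.

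A reader might also infer that the discrepancy is an artefact, because the outer edges of the imaged foci can match the pathological size exactly. That does not follow. Entry before surgery requires imaging to show at least 2 cm of normal tissue between the foci. If pathology finds one continuous lesion, imaging missed disease in that gap. This is a real under-call of extent, and comparing span with span alone would score it as perfect agreement.

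Three further objections stand in part. Keeping these women here while 16.61 excludes them is no inconsistency, because imaging accuracy and local recurrence are different questions. A contiguous case may be conspicuous on the plot: -32 mm is four times the assumed SD of 8 mm. And an imaged span cannot always be derived: a lesion may be visible on MRI only, and lesion sizes plus one shortest distance do not fix the span when diameters lie off the joining line or there are three foci.

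None of this supplies a pairing rule, a unit of analysis or an allowance for clustering.

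**Conclusion.** The concern holds as a gap in specification. The lesion-level comparison includes women whose lesions cannot be matched one to one, without a pairing rule, and the z-interval makes no allowance for lesions from the same woman. Under the assumptions shown, the choice of pairing moves the mean by up to 3.2 mm and the spread from 15.7 to as much as 24.5 mm (set A). If one pathology lesion is used twice, the standard error is too small by a factor of 1.15 to 1.26 in set A, by 1.28 or more in set B with s = 0.5 cm and p of 5% or above, and by as little as 1.07 with s = 1.0 cm and p = 2%. If the ordinary errors of lesions in one woman are positively correlated, the interval is too narrow even without contiguous cases.

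The documents give neither the contiguous share nor the SD, so these figures show direction and plausible size only. The analysis serves a correlative goal; the primary endpoint and the stopping rules are untouched.

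**What to change.** Amend section 16.664 as follows.

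1. Base the lesion-level Bland-Altman comparison on lesions that match one to one between mammogram and pathology. Show it with and without contiguous cases, and state in advance the pairing used when they are included. Apply the same matching rule to location agreement and to lesions not seen on mammogram.
2. Report the number and proportion of women whose separate imaged foci were one contiguous lesion, as a discordance between imaging and pathology in its own right. Add a comparison of imaged span with pathology size only as a supplement, where the span can be measured on the centrally reviewed images.
3. Compute the confidence interval, and any limits of agreement, with woman as the cluster. Say whether the z-interval is for the mean difference or is meant as limits of agreement.

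The cost is a few sentences, slightly more analysis work and a somewhat wider interval. Items 1 and 3 use sizes and locations that the plan already obtains. For item 2, section 7.3 already requires pathology to assess separateness when lesions are excised en bloc; the supplementary span needs one further measurement on images already held.

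### Section 16.664 makes no allowance for several lesions from one woman, names no limits of agreement for lesion size, and answers goal 2.32 for mammography only

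*Combined protocol and SAP*

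**What the plan says.** Goal 2.32, listed among the correlative goals, is broad: "To compare the extent of disease described on imaging (mammography, bilateral breast MRI and other adjunctive imaging modalities) with surgical findings".

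Section 16.664 is the analysis that serves it, and it deals with mammography.

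- **Population:** "All eligible patients who have initiated surgery will be included in the analysis of this endpoint".
- **Measurement:** "The maximum lesion dimension and location of each lesion found on mammogram will be determined on central review".
- **Size:** a Bland-Altman plot of difference against average, described as a check for systematic bias, and then: "A 95 % z-confidence of the difference in lesion size between that found on mammogram and that found on surgery will be constructed".
- **Location:** percent agreement, without an interval.

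Two other sections determine what data reach this analysis. Section 3.14 requires "two or three foci of biopsy proven breast cancer separated by ≥ 2 cm of normal breast tissue" and admits lesions that are "visualized on MRI but not on mammogram OR visualized on mammogram but not on MRI". Sections 3.14 and 7.3 also let a patient stay on study if, at pathology, "two or three lesions identified on pre-operative imaging represent one contiguous lesion".

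Section 16.664 does not say whether the lesion or the woman is the unit of analysis. It does not say how imaged and pathological lesions are paired, or what happens to a lesion that appears on only one side of the comparison.

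**The concern.** Four things need attention.

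1. Sizes are recorded per lesion, and eligibility ensures that most women bring more than one. The same breast, mammogram, central reading and pathology department lie behind each woman's lesions, so her size differences may resemble each other. A z-interval with the ordinary standard error would then be too narrow.
2. An interval for a mean difference answers whether mammography over- or under-sizes on average. It does not say how far a single mammographic size may lie from the pathological size, which is what a surgeon planning an excision would want to know.
3. A lesion that mammography missed has no mammographic size. The size comparison is therefore conditional on detection, and read alone it would flatter mammography.
4. Goal 2.32 names MRI and other modalities, and Section 16 contains no analysis of them against surgical findings.

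At stake is how the imaging result is read: its precision, its meaning for an individual lesion, and whether the stated goal is met.

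**Working it through.** Section 16.664 gives no sample size, standard deviation or target precision, so it has no figure to reproduce.

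**Inputs from the documents.** Two or three foci per woman (3.14); 200 evaluable patients and a target accrual of 265 (16.3).

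**Assumptions, because the documents give no values.** The within-woman correlation ρ of the size differences, and the mix of women giving one, two or three mammogram-pathology pairs.

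**Clustering.** With m pairs per woman and m_A = Σm²/Σm:

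- design effect = 1 + (m_A − 1)ρ
- true SE / naive SE = √(design effect)
- coverage of the naive 95% interval = 2Φ(1.96/√(design effect)) − 1

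The values of m_A are:

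- all women with two pairs: 2
- 90% with two and 10% with three: (0.9×4 + 0.1×9)/(0.9×2 + 0.1×3) = 4.5/2.1 = 2.143
- half with one and half with two: (0.5×1 + 0.5×4)/(0.5×1 + 0.5×2) = 2.5/1.5 = 1.667

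| Pairs per woman | ρ | Design effect | True SE / naive SE | Coverage |
|---|---|---|---|---|
| any mix | 0 | 1.000 | 1.00 | 95.0% |
| all 2 | 0.2 | 1.200 | 1.10 | 92.6% |
| all 2 | 0.5 | 1.500 | 1.22 | 89.1% |
| 90% 2, 10% 3 | 0.2 | 1.229 | 1.11 | 92.3% |
| 90% 2, 10% 3 | 0.5 | 1.571 | 1.25 | 88.2% |
| half 1, half 2 | 0.2 | 1.133 | 1.06 | 93.4% |
| half 1, half 2 | 0.5 | 1.333 | 1.15 | 91.0% |

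A negative correlation reverses the effect: at ρ = −0.1 with two pairs each, coverage is 96.1%.

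A simulation of 200 women, 10% with three lesions, in 8,000 runs agreed with the formula. Naive coverage was 92.7% at ρ = 0.2 and 88.2% at ρ = 0.5. A patient-clustered standard error gave 95.2% and 95.0%. The pooled standard deviation of the differences was almost unaffected (0.998 to 0.999 of its true value). Clustering therefore matters for the interval around the bias, and for any intervals around limits of agreement, but hardly for the limits themselves.

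**Bias versus spread.** If the interval is for the mean, its half-width is 1.96·SD/√n; limits of agreement have half-width 1.96·SD. For normal differences centred on the estimated mean, the share of individual differences inside the interval for the mean is 2Φ(1.96/√n) − 1:

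- n = 200 pairs (200 women, one pair each): 11%
- n = 400 (200 women, two each): 8%
- n = 530 (265 women, two each): 7%

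This follows from √n alone and says nothing about how large the size errors in this trial will be. It shows only that the two summaries answer different questions. The choice of z over t is immaterial here: the critical values differ by 0.6% at n = 200.

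**Detection and pairing.** All eligible patients who started surgery enter the analysis, but a difference in size exists only for a lesion measured on both sides. A focus seen on MRI alone gives no difference, and two imaged foci that are one lesion at pathology give two mammographic sizes against one pathological size. Section 16.664 covers neither case.

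**Modalities.** Mammography is mandatory and MRI optional (7.1, 7.12). Where MRI was done, images go to central review (7.12, 7.15) and an on-study MRI form is required (18.2). So material for an MRI comparison is being collected.

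**The case against.** The best defence is that much of this is silence. Section 16.664 never says that lesions will be treated as independent and gives no standard-error formula, so a careful analyst could cluster by patient without departing from it. That stands: a reader might infer that independence has been assumed, but the documents show only that handling within a woman is unspecified. Nor can one say that the interval will be too narrow. That needs a positive correlation, which the documents do not give, and the effect shrinks when women contribute a single pair.

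The key sentence also lacks the words for an interval and for a mean. Since Bland and Altman's approach is named just before it, mean ± 1.96 SD cannot be ruled out. A confidence interval is the likelier reading, because Sections 16.61, 16.62, 16.65 and 16.66 use the same pattern of a distribution name followed by a confidence interval. On either reading the sentence needs completing.

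A reader might go further and infer that agreement is not measured at all. The documents do not support that. The planned plot displays the scatter of individual differences, so a badly mis-sized lesion would be visible, and location has percent agreement. What is missing is a number for the spread in size.

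Finally, MRI is optional while every woman has a mammogram, so making mammography the main comparison is defensible. That explains the emphasis, but it does not reconcile 16.664 with a goal that names MRI.

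**Conclusion.** The concern holds as under-specification with a modest numerical consequence. For ρ of 0.2 to 0.5 and about two lesions per woman, an unadjusted interval would have a standard error too small by a factor of about 1.1 to 1.25 and would cover about 93% to 88%. With half the women giving one pair, coverage is about 93% to 91%, and at zero correlation there is no error. These figures rest wholly on the assumed correlation and lesion mix.

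Three parts need no such assumption. No limits of agreement are named, so the spread for individual lesions is shown on a plot but not quantified. The size comparison is conditional on the lesion being seen on mammogram, with no rule for those that were not. Goal 2.32 is answered for mammography only. It would be too strong to call the goal unanswered, because the mammography part is planned in reasonable detail.

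The comparison is correlative, is not among the endpoints in Section 16.2, and carries no test or stopping rule. The primary endpoint is unaffected.

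**What to change.** Amend 16.664 as follows.

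- State that the lesion is the unit of measurement, and give the rule for pairing mammographic with pathological lesions, including foci found to be contiguous at pathology.
- Give the mean size difference with a patient-clustered 95% confidence interval, from a random-intercept model or a bootstrap that resamples patients.
- Report 95% limits of agreement, with confidence intervals that allow for multiple lesions per woman.
- Alongside the size results, report the proportion of pathology-confirmed lesions not visualised on mammogram.
- Apply the same analysis to MRI in women who had one, with the number of such women stated, so that 16.664 matches goal 2.32 more closely.

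The cost is SAP wording and a little more analysis work, and no new data are needed for the mammography or MRI comparison. Intervals will be slightly wider if the within-woman correlation is positive. The MRI results will describe only the women selected for that examination and should be presented as such.

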16.3 Sample Size Determination

Assuming a cohort of 200 eligible patients is enrolled over a 2 year period, the follow-up period after the close of enrollment is 5 years, and the number of local recurrences follows a Poisson distribution, the upper bounds of 95 % confidence interval for the cumulative incidence of a local recurrence within 5 years would fall below 8 % if at most 8 local recurrences occurred as a first event among these 200 patients.

It was originally planned to have an additional 30 patients enrolled to account for patients who withdraw consent prior to surgery, are found to be ineligible after signing a consent form, convert to mastectomy, or are found to have a single contiguous area of malignancy at final pathology. During the course of the study, it was found that many patients were being deemed ineligible after enrollment because the distance between lesions was outside the allowable range. This caused a high rate of ineligibilities. The protocol was amended and the ineligibility rate has subsequently decreased. However, in order to obtain the 200 evaluable patients needed for the primary endpoint, the study will need to enroll a total of 265 (35 additional) patients. Hence the target accrual for the study is 265 patients.

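### The only planned number for mammogram–pathology size agreement is, read naturally, an interval for mean bias; limits of agreement and clustering by woman should be added

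*Combined protocol and SAP*

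**What the plan says.** Section 16.664 serves correlative goal 2.32, the comparison of imaging extent with surgical findings. It works lesion by lesion: "The maximum lesion dimension and location of each lesion found on mammogram will be determined on central review". Size agreement with the pathology report "will be examined using the approaches proposed by Bland and Altman". The text then describes a plot of the average of the two sizes against their difference, which "will be constructed to examine systematic biases", and adds: "A 95 % z-confidence of the difference in lesion size between that found on mammogram and that found on surgery will be constructed". Location is handled separately, by percent agreement.

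The population is broad: "All eligible patients who have initiated surgery will be included in the analysis of this endpoint". Eligibility under 3.14 calls for "two or three foci of biopsy proven breast cancer separated by" at least 2 cm of normal tissue, so each woman normally brings more than one lesion.

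The section does not name limits of agreement. It does not say whether the z-interval concerns the mean or individual differences, and it does not say how several lesions from one woman are combined.

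**The concern.** Agreement between two measurements has two parts: average bias, and the spread of individual differences around it. An interval for the mean difference addresses only the first. Over- and under-measurement cancel in it, and its width falls with the square root of the number of lesions however large the individual errors are. If it is the only number reported, a reader learns how precisely the average bias is known and nothing about how far a single lesion's mammographic size may be from its pathologic size. Goal 2.32 needs that second quantity.

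The second issue is the unit of analysis. Lesions from one woman share the same imaging examination and, usually, the same pathology service. If their size differences are positively correlated, a z-interval computed as though every lesion were independent is too narrow.

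**Working it through.** The plan gives no sample size, SD, acceptable difference or within-woman correlation for this analysis, so it has no figure of its own to reproduce. The check below uses the documents' counts and states every assumption.

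**Inputs from the documents**
- Unit: the lesion (16.664).
- Foci per woman: two or three (3.14).
- Women: between the 200 in "in order to obtain the 200 evaluable patients needed for the primary endpoint" and the full enrolment in "Hence the target accrual for the study is 265 patients" (both 16.3).

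**Assumed**
- SD of the size difference: 5, 10 or 15 mm.
- Mammogram–pathology pairs: 200 × 2 = 400 as base case, and up to 265 × 3 = 795 if every focus could be paired.
- Within-woman correlation ρ of the differences: 0 to 0.5.

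**Step 1: interval for the mean against limits of agreement**

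The half-width of the z-interval for the mean is 1.96 × SD / √n. The half-width of the 95% limits of agreement is 1.96 × SD. With n = 400, √n = 20:

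| Assumed SD | Interval for mean | Limits of agreement |
|---|---|---|
| 5 mm | ±0.49 mm | ±9.8 mm |
| 10 mm | ±0.98 mm | ±19.6 mm |
| 15 mm | ±1.47 mm | ±29.4 mm |

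The ratio of the two is √n whatever the SD: 20 at 400 lesions and 28 at 795. With SD 15 mm and no bias, the share of lesions differing by more than 10 mm is 2 × (1 − Φ(10/15)) = 0.50, while the interval for the mean is still only about ±1.5 mm.

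**Step 2: clustering**

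With m pairs per woman the design effect is 1 + (m − 1)ρ. The true coverage of an interval that ignores clustering is 2Φ(1.96/√(design effect)) − 1.

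| Assumed ρ | Coverage, m = 2 | Coverage, m = 3 |
|---|---|---|
| 0 | 95.0% | 95.0% |
| 0.1 | 93.8% | 92.6% |
| 0.3 | 91.4% | 87.9% |
| 0.5 | 89.0% | 83.4% |

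For m = 2 the standard error should be larger by a factor of 1.05, 1.14 and 1.22 at ρ = 0.1, 0.3 and 0.5. At a negative correlation of −0.2 the plain interval would be too wide (97.2% coverage).

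**Step 3: women who supply only one pair**

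Section 3.14 admits lesions seen on MRI but not on mammogram. Sections 3.14 and 7.3 keep women whose foci prove to be one contiguous lesion. With unequal numbers of pairs the design effect is 1 + ρ(Σm²/Σm − 1). If half of 200 women supply one pair and half supply two, Σm = 300 and Σm² = 500. At ρ = 0.3 the design effect is 1 + 0.3 × 0.667 = 1.20 and coverage is 92.6%, against 91.4% when all supply two.

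**Step 4: simulation check**

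A simulation with 200 women, two pairs each, SD 10 mm and 4,000 runs per setting gave plain-interval coverage of 94.5%, 93.6%, 92.1% and 89.4% at ρ = 0, 0.1, 0.3 and 0.5. That is consistent with Step 2. An interval computed from woman-level means covered 94.5% to 95.6%. The limits of agreement themselves hardly moved with clustering: mean half-width was 19.56 to 19.61 mm over the same range.

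**The case against.** A reader might infer that the plan will make poor agreement look good. The documents do not support that. Section 16.664 invokes the Bland-Altman approach and plans the plot, and with the SDs above the wide scatter would be plain on it. Nothing in the section sets zero as a benchmark, plans a test, or says that an interval containing zero will be read as agreement. Any valid 95% interval contains a true zero bias 95% of the time, so that fact alone is no defect. The risk is one of reporting: the single number could be quoted without the plot.

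The sentence on the z-interval also lacks its noun and does not contain the word mean. Under a Bland-Altman citation it could denote mean ± 1.96 SD, the limits of agreement. If so, spread would be described and clustering would hardly matter to the limits. I still take the confidence-interval reading as the natural one, because the other analyses in 16.6 construct 95% confidence intervals for a parameter. If limits were meant, the text needs to say so.

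A reader might also infer that the plan assumes independent lesions and that the interval is certainly too narrow. The section is silent on independence. Narrowing needs a positive correlation, for which the documents give no value; at zero there is none, and at 0.1 with two pairs the loss is about one percentage point. Pairs will also be fewer than foci for some women, so 400 is an assumption and not a count.

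What stands is that no named number describes individual disagreement, the target of the interval is unclear, and clustering is not addressed.

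**Conclusion.** The point holds as a cheap improvement of minor severity. On its natural reading the interval in 16.664 quantifies average bias only, and it would be 20 to 28 times narrower than the limits of agreement for 400 to 795 paired lesions. The millimetre figures depend on assumed SDs; the ratio depends only on the number of pairs. The undercoverage from ignoring clustering runs from nothing at zero correlation to about 6 percentage points at 0.5 with two pairs per woman. It is larger with three pairs and smaller where women supply one.

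This is a descriptive analysis for a correlative goal, with no decision rule attached. The local-recurrence conclusion does not depend on it.

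**What to change.** In 16.664:

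- Keep the plot and add Bland-Altman 95% limits of agreement, with confidence intervals, as the summary of size agreement.
- State that the z-interval is for the mean bias, and compute it clustered by woman, using a mixed model with a random woman effect or a patient-level bootstrap. With the mixed model, base the limits on the total SD (between-woman plus within-woman variance).
- State that a bias interval containing zero will not be taken as evidence of agreement.

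The cost is a few sentences and a few lines of code on data already being collected. The bias interval becomes slightly wider if the correlation is positive: in the simulation with SD 10 mm and two pairs per woman, its full width rose from 1.96 mm to 2.06 mm at a correlation of 0.1 and to 2.39 mm at 0.5.
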